1 INTRODUCTION

The *Dynesys*® dynamic stabilization system is a pedicle screw system that has been in clinical use for about 16 years. It consists of titanium alloy pedicle screws, coated and un-coated with hydroxyapatite, set screws, polycarbonate urethane (PCU) spacers and polyethylene terephthalate (PET) cord. The Zimmer DTO Implant, consisting of a titanium alloy rod and PET cord, was introduced in 2007 to allow connection of the Dynesys dynamic system to the Optima rigid pedicle screw system.

The Dynesys components consist of the following materials:

- Pedicle screw made of Titanium alloy (PROTASUL-100) according to ISO 5832-11
- Set screw made of Titanium alloy (PROTASUL-100) according to ISO 5832-11
- Spacers made of Sulene® PCU (Polycarbonate-urethane).
- Cord made of Sulene® PET (Polyethylene-terephthalate)
- DTO Implant made of of Titanium alloy (PROTASUL-100) according to ISO 5832-11 and Sulene® PET (Polyethylene-terephthalate)

One of the markets in which Dynesys is sold is the United States. The US medical device regulatory body, FDA, has ordered that a post-market surveillance study be conducted on all Dynesys device configurations for the US cleared indication as an adjunct to fusion. As part of this post market surveillance study FDA has mandated an analysis of all Dynesys explants received worldwide to identify possible failure modes, the clinical circumstances in which failure is occurring, and associated patient demographics.

2 OBJECTIVE

The goal of this study is to perform retrieval analysis [1-3] on all explants received at Zimmer, including the identification of structural failures in failed components. Structural failures are classified as fractured pedicle screws, set screws or Titanium rods, rupture of PET cords, or fracture and cracking of PCU spacers that lead to malfunction or non-function of the components or the system.

3 HANDLING of RETRIEVALS

Revision surgery: A patient outside the US needs to give his/her written consent that he/she agrees that the explants will be used for investigation which might include adverse modification or destructive testing of the explants [8]. If the patient agrees to the investigation of his/her explants the rights of ownership and storage of the retrievals will be handed over to Zimmer GmbH.

From US patients no written patient consent for explant analysis is required even if the investigation might include adverse modification or destructive testing.

All removed Dynesys parts must be fully traceable back to the instrumented levels and side of vertebra. All retrieved implants of a received system must be sent back to Zimmer.

Cleaning, disinfection, sterilization: Immediately after removal the explanted Dynesys parts must be carefully cleaned by rinsing under cold (<20°C) tap water (no brushing). The components should be free of attached soft tissue after cleaning. The components must not be treated with any cleaning agent; an investigation may not be possible if a cleaning agent is used. It is possible to

autoclave the screws. The PCU spacers, the PET cords and DTO implant must not be autoclaved; if they are autoclaved an investigation is not possible.

Storage and shipment condition: All components should be dried in air with no additional heat. The components should be packaged individually in plastic bags and labeled with patient's identifier and instrumented levels e. g. patient initials or ID, L5, right.

General information: The following information is needed to do a full retrieval assessment at Zimmer GmbH:

Patient: initials or patient ID, gender, birthday, body mass index or height and weight

Clinical: implantation date, revision date, reason for revision, treated segments, name of surgeon, name and address of hospital/clinic, surgical notes, x-rays

Product information: REF number and LOT number from the spacers and cords. This information is only available from the implantation of the device (patient chart stickers) and not on the device itself. Without this information no conclusions may be drawn about the impact of manufacturing on the explants.

Note: The quality of the retrieval analysis depends on the quality of data we receive from the hospital and from the quality of the explanted Dynesys parts. Wrong handling of the retrieved components or missing information can influence the quality of the analysis; under certain conditions the investigation can not be performed. For retrievals coming from patients outside the US a written consent of the patient has to be at hand to conduct adverse modification or destructive testing of the explants. Without written patient consent only visual inspection can be performed.

4 MATERIALS and METHODS

4.1 Material

All retrievals received at Zimmer.

4.2 Methods

4.2.1 General

The following methods will be used for the specific investigation of the single parts of the Dynesys system.

Component	Used investigation methods
Pedicle screw	Visual inspection
	Low power light microscope
	Scanning Electron Microscopy (SEM) (if necessary and / or of interest)
Set screw	Visual inspection
	Low power light microscope
	SEM (if necessary and / or of interest)

Spacer	Visual inspection
	Low power light microscope
	SEM (if necessary and / or of interest)
	Attenuated Total Reflection Fourier Transform Infrared Spectroscopy (ATR-FTIR)
	Gel Permeation Chromatography (GPC)
Cord	Visual inspection
	Low power light microscope
	SEM (if necessary and / or of interest)
	ATR-FTIR
	GPC
DTO Implant	Visual inspection
	Low power light microscope
	SEM (if necessary and / or of interest)
	ATR-FTIR for the cord only
	GPC for the cord only

4.2.2 Sample preparation

Pedicle and set screws will be disinfected by the following steps:

- soaking at room temperature in a 4% disinfective solution (Deconex 53 plus, Borer Chemie AG, Zuchwil Switzerland) for 30 minutes ± 5 minutes
- rinsing with cold (<20°C) tap water
- soaking in industrial ethyl alcohol (96%) for one hour ± 10 minutes.
- rinsing with cold (<20°C) tap water
- autoclaving at 134°C for 18 min

Spacers, cords and DTO implants will be disinfected by the following steps:

- soaking at room temperature in a 4% disinfective solution (Deconex 53 plus, Borer Chemie AG, Zuchwil Switzerland) for 30 minutes ± 5 minutes
- rinsing with cold (<20°C) tap water

These steps will be repeated three times.

4.2.3 Visual inspection

Visual Inspection

All explanted components will be visually inspected by the naked eye. Areas of interests are: contact areas, fractured surfaces, wear/tear, surface cracks, discoloration, deformation, or other interested phenomena. Photographical documentation of the components will be performed if it helps for clarification or documentation.

Low Power Light Microscope

This method allows documentation of areas of interest on the components up to 40X.

SEM

The method of the SEM allows two functions: (1) imaging of areas of interest with high magnification and (2) semi-quantitative analysis of elemental composition of areas of interest. SEM enables a profound analysis of fractures, wear, and cracks.

(1) Imaging of surface: High-powered electron beam that produces an image with secondary electrons (SE) or back-scattered electrons (BSE). Polymer materials must be sputter coated before with a thin layer of carbon or gold. This method will be used if the magnifications of 40X provided by the low power light microscope is not sufficient perform a full analysis of areas of interest.

(2) Elemental analysis: The technique is energy dispersive X-ray analysis (EDX) to identify elemental composition of small areas. Polymer materials must be sputter coated before with a thin layer of carbon or gold.

4.2.4 ATR-FTIR Analyses of PET Cords

Fracture, rupture and cracking of polymeric components originates at the molecular level due to the chemical changes that result from the chemical reactions between polymeric components and the environment of the human body. ATR-FTIR Analyses will produce spectra readings that reveal the chemical structures of the polymer. If there are changes in the chemical structures this may be indicative of changes and breakage of molecular bonds. PET cord samples will be placed on an ATR cell, and the spectra will be recorded using an FTIR with a scan range of 400-4000 cm^{-1} and a scan resolution of 4 cm^{-1} . FTIR spectra will be taken from a minimum of two different locations at the PET cord: (1) on the outer woven cord surface, and (2) on the center fibers of cord.

To evaluate the differences in all the spectra and to assess the absence of residual tissue, the spectra will be normalized to the band of a chemically stable aromatic group (725 cm^{-1}) and compared to the spectra of a non-implanted reference PET cord. Control (reference) specimens will be current-production parts.

To evaluate the possible chemical change of the PET cord due to hydrolytic degradation, the carboxyl index, i.e., the absorbance ratio of the carboxylic acid (1640 cm^{-1}) to the carbonyl group (1713 cm^{-1}), will be calculated. To minimize the interference from the protein bands of residual tissues, only the spectra that have weak or no protein bands at 1520-1540 and 1650 cm^{-1} will be recorded.

4.2.5 ATR-FTIR Analyses of PCU Spacers

Fracture, rupture and cracking of polymeric components originates at the molecular level due to the chemical changes that result from the chemical reactions between polymeric components and the environment of the human body. ATR-FTIR Analyses will produce spectra readings that reveal the chemical structures of the polymer. If there are changes in the chemical structures this may be indicative of changes and breakage of molecular bonds. PCU spacer samples will be placed on an ATR cell, and the spectra will be recorded using a FTIR with a scan range of 400-4000 cm^{-1} and a scan resolution of 4 cm^{-1} . The ATR-FTIR spectra of PCU spacers will be specifically collected from at least three sample locations: (1) on the spacer surface, (2) 100 μm below the surface and (3) in the bulk of spacer. Because the surface chemistry of polyurethanes may vary in the air environment, spectra of the bulk spacer samples will be recorded immediately after cutting them.

All spectra will be normalized to the chemically stable aromatic group (510 cm^{-1}). Subsequently, the spectra will be compared to a representative non-implanted reference PCU spacer. Control (reference) specimens will be current-production parts.

The percentage differences in peak height of the retrieval samples to the reference PCU sample will be quantified using the following peaks: (1) NH ($\sim 3340\text{ cm}^{-1}$) and (2) hydrogen-bonded C=O ($\sim 1701\text{ cm}^{-1}$) of urethane hard segment, (3) free C=O ($\sim 1740\text{ cm}^{-1}$) and (4) C-O-C ($\sim 1248\text{ cm}^{-1}$) of carbonate soft segment, and (5) the broad band at $3200\text{-}3500\text{ cm}^{-1}$ (measured at $\sim 3280\text{ cm}^{-1}$) corresponding to the increase in NH and OH of degraded urethane and carbonate or to absorbed biofluid.

4.2.6 GPC Analyses of PET Cords

Gel Permeation Chromatography will produce spectra identifying the molecular weight and distribution of the PET polymer. Molecular changes may be indicative of bond breakages. The PET cord samples (on the outer woven cord surface, and on the center fibers of cord) will be completely dissolved in hexafluoroisopropanol (3 g/L) with 0.05M potassium-trifluoroacetate. The chromatography is done in a PSS-PFG 7 μm column or comparable. Poly(methyl-methacrylate) standards will be used for calibration.

The weight average molecular weight (M_w), number average molecular weight (M_n), and the polydispersity indices (PDI, the ratio of M_w to M_n) will be calculated. The results will be compared to a representative non-implanted reference PET cord. Control (reference) specimens will be current-production parts.

4.2.7 GPC Analyses of PCU Spacers

Gel Permeation Chromatography will produce spectra identifying the molecular weight and distribution of the PCU Spacer polymer. Molecular changes may be indicative of bond breakages. The PCU samples (on the spacer surface of 0-100 μm below the surface, and in the bulk of spacer) are dissolved in dimethylacetamide (3 g/L) with 0.1% of LiBr at 80°C. The chromatography is done in a PSS-GRAM 10 μm column or comparable. Polystyrene standards will be used for calibration.

The weight average molecular weight (M_w), number average molecular weight (M_n), and the polydispersity indices (PDI, the ratio of M_w to M_n) will be calculated. The results will be compared to a representative non-implanted reference PCU spacer. Control (reference) specimens will be current-production parts.

4.3 Test method and sample size rationale

Component	Used investigation methods	Sample selection including rationale
Pedicle screw	Visual inspection	All
	Low power light microscope	All
	SEM (if necessary and / or of interest)	Fracture surfaces
Set screw	Visual inspection	All
	Low power light microscope	All
	SEM (if necessary and / or of interest)	Special phenomena (e.g., cracks)
Spacer	Visual inspection	All (discoloration, deformation, surface)
	Low power light microscope	All
	SEM (if necessary and / or of interest)	Contact areas, worn areas, surface cracks
	ATR-FTIR	Analysis only performed on samples ≥ 12 months because no significant changes were identified up to 19 months in-vivo [4-6]. One contact area, one non-contact area and if available a worn area of one

		
representative sample.
 
It is assumed that all spacers of a system are subjected to the same body environment (same body fluid, body temperature etc.) resulting in the same material behavior for all spacers.

	GPC	
Analysis only performed on samples \geq 12 months because no significant changes were identified up to 19 months in-vivo [4-6].
 
One non-contact area of one representative sample.
 
It is assumed that all spacers of a system are subjected to the same body environment resulting in the same bio-stability behavior for all spacers.

Cord	Visual inspection	All (surface, worn areas)
	Low power light microscope	All
	SEM (if necessary and / or of interest)	Contact areas, worn areas, cord ruptures
	ATR-FTIR	
Analysis only performed on samples \geq 12 months because no significant changes were identified up to 19 months in-vivo [4, 5, 7].
 
One contact area, one non-contact area and if available a worn area of one representative sample.
 
It is assumed that all cords of a system are subjected to the same body environment resulting in the same material behavior for all cords.

	GPC	
Analysis only performed on samples \geq 12 months because no significant changes were identified up to 19 months in-vivo [4, 5, 7].
 
One non-contact area of one representative sample.
 
It is assumed that all cords of a system are subjected to the same body environment resulting in the same bio-stability behavior for all cords.

DTO implant	Visual inspection	All (contact areas, worn areas, fracture surfaces)

	Low power light microscope	All
	SEM (if necessary and / or of interest)	Contact areas, worn areas, cord ruptures or rod fractures
	ATR-FTIR for the cord only	
Analysis only performed on samples ≥ 12 months because no significant changes were identified up to 19 months in-vivo [4, 5, 7].
 
One contact area, one non-contact area and if available a worn area of one representative sample.
 
It is assumed that all cords of a system are subjected to the same body environment resulting in the same material behavior for all cords.

	GPC for the cord only	
Analysis only performed on samples ≥ 12 months because no significant changes were identified up to 19 months in-vivo [4, 5, 7].
 
One non-contact area of one representative sample.
 
It is assumed that all cords of a system are subjected to the same body environment resulting in the same biostability behavior for all cords.

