APPENDIX A: EXPLANT ANALYSIS PROTOCOL	
APPENDIX B: IMAGING PROTOCOL	

APPENDIX C: INSTRUCTIONS FOR USE

APPENDIX D: SURGICAL TECHNIQUE

APPENDIX E: INFORMED CONSENT

APPENDIX F: CASE REPORT FORMS

PROTOCOL SUMMARY

Title	Post Market Surveillance for the Dynesys® Spinal System, Assessing Safety and Fusion.
Device	The Dynesys® Spinal System
Study Purpose	To assess the safety profile and fusion rates following posterior lateral fusion with the Dynesys® Spinal System as an adjunct to fusion compared to a literature control.
Study Design	
This is a prospective, non-randomized study involving up to 168 subjects at up to 12 investigative centers. Each subject will be an appropriate candidate for an instrumented, pedicle screw implantation and will meet the inclusion and exclusion criteria defined in Section III. Patients will receive either (1) Dynesys/Dynesys Top Loading with autograft at the instrumented levels, as an adjunct to fusion, or (2) Zimmer DTO Implant with autograft at the instrumented levels, as an adjunct to fusion and will be compared to a literature control.
 
Data will be collected pre-operatively, operatively and post-operatively at six, twelve and twenty-four months. Patients will be followed annually thereafter until the last patient has completed follow-up. This study will be conducted in compliance with the protocol, GCP and applicable regulatory requirements.

Enrollment Size	Up to 168 subjects at up to 12 investigative centers
Patient Population	Patients who are candidates for a PLF procedure and meet the inclusion/exclusion criteria are eligible for enrollment.
Endpoints	
Determine the fusion rates at every treated level.
 
For adverse events at every treated level:
 
 • Determine the incidence rates. • Determine the severities. • Determine the time course. 
For subsequent surgical procedures at every treated level:
 
 • Determine the types of surgical procedures that are required. • Determine the incidence rates. • Determine the time course. 
Based on explanted, retrieved devices:
 
 • Determine the failure modes. • Determine the causes of failure.

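### Appendix A rules out ATR-FTIR and GPC for polymer parts that fail before 12 months, and after 12 months does not ensure that the failed part is the one tested

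*Combined protocol and SAP*

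**What the plan says.** The Protocol Summary and Section I.B list, for retrieved explants, failure modes and also "Determine the causes of failure". Section V.C repeats both as an analysis commitment.

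Appendix A, Sections 4.2.4 and 4.2.5, introduces the spectroscopy with the premise "Fracture, rupture and cracking of polymeric components originates at the molecular level due to the chemical changes" that follow from reactions with the body. Sections 4.2.6 and 4.2.7 use GPC to look for molecular changes that may indicate broken bonds.

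Section 4.3 then sets who gets these tests. The spacer, cord and DTO-cord rows for both tests open with "Analysis only performed on samples" of 12 months or more, and the reason given is "because no significant changes were identified up to 19 months in-vivo". For eligible systems:

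- ATR-FTIR takes "One contact area, one non-contact area and if available a worn area of one" representative sample.
- GPC takes "One non-contact area of one representative sample".
- The justification for cords is "It is assumed that all cords of a system are subjected to the same body environment resulting in the same material behavior for all cords". The spacer rows reason the same way: "It is assumed that all spacers of a system are subjected to the same body environment".

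Visual inspection and light microscopy cover every component at any implant time. SEM is optional, has no time limit, and names cord ruptures and spacer surface cracks among its targets.

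**The concern.** Both restrictions are reasonable for intact retrievals. They fit poorly with a part that has broken, and broken parts are what the cause-of-failure objective is about.

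The 12-month limit rests on what was seen in previous retrievals taken together. A cord that ruptured at, say, 8 months may be the exception which that experience does not describe, and the rule leaves no way to find out by polymer chemistry. The one-part rule rests on all like parts of a system behaving alike. If one cord has ruptured and its partner has not, they have visibly not done so.

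At stake is whether the final report can say anything about material degradation as a cause of an early polymer failure, and whether a later chemical result comes from the part that failed.

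**Working it through.** The plan gives no figure for this point, so the check sets its own provisions side by side.

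**1. Objective against deliverable.** The protocol (Summary, I.B, V.C) asks for causes as well as modes. Appendix A, Section 4.4, undertakes only to document the condition of the retrievals and to identify structural failures. Causes are not mentioned there.

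**2. Premise against test rule.** Sections 4.2.4 and 4.2.5 place the origin of polymer failure in chemical change. ATR-FTIR and GPC are the tests that the appendix provides for polymer structure and molecular weight. Section 4.3 withholds both below 12 months. The spacer, cord and DTO-cord rows contain no exception for a structural failure.

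**3. The time limit against its evidence.** No change was reported up to 19 months and testing starts at 12, so the limit lies 19 − 12 = 7 months inside the no-change period. It is stricter than its rationale requires. The documents do not say whether the supporting retrievals included ruptured cords or cracked spacers, so how far the evidence covers failed parts is unknown.

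**4. Length of the untested window.** Fusion is assessed at 24 months (Section V.B). Twelve of those 24 months have no ATR-FTIR or GPC for any explanted polymer part. The appendix also covers explants received worldwide (its Section 1). Neither document gives an expected number of early polymer failures, so this window cannot be turned into a count.

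**5. Sampling from 12 months.** The term *representative* is not defined. The text neither requires nor excludes the failed part. Within the chosen part, ATR-FTIR covers contact, non-contact and, if available, worn areas. GPC covers a non-contact area only, although Sections 4.2.6 and 4.2.7 sample it both at the surface and deeper in.

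**6. A trigger already exists.** Section 2 of Appendix A defines structural failure, including rupture of PET cords and fracture or cracking of PCU spacers. Section 4.3 points SEM at failure sites but does not use the definition to trigger ATR-FTIR or GPC.

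**7. What remains before 12 months.** Visual inspection, light microscopy and, if judged necessary or of interest, SEM with EDX (Section 4.2.3). EDX gives elemental composition, not polymer chain length or bond chemistry.

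**The case against.** The strongest reply is that the gap is narrow. The laboratory inspects every part, so it can see which one failed and may choose it as the representative sample. SEM can examine ruptures and cracks at any implant time. Surgical notes, x-rays, the reason for revision and lot numbers are collected as well. Section 5 lets the 12-, 24- and 36-month summary reports propose additional tests. All of this stands. However, choosing the failed part remains optional, and a proposal in a later report makes no provision for early failures already received.

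A reader might infer more than the documents support:

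- *That early failures get no chemical analysis at all.* EDX is available without a time limit. What is missing is ATR-FTIR and GPC.
- *That an intact part is tested in place of the failed one.* Section 4.3 does not say so.
- *That causes cannot be determined.* Microscopy and SEM can support mechanical causes, and later systems do get ATR-FTIR and GPC.
- *That a normal result would be read as absence of degradation.* Section 4.4 sets no acceptance criteria. Before 12 months there is no result to misread, and the omission of loaded areas applies to GPC only.
- *That the failed part is usually missed.* With one failed spacer among k and a choice made without regard to failure, the chance of missing it is 1 − 1/k. Assuming two spacers per level, that is 50% for one level (k = 2), 75% for two (k = 4) and 83% for three (k = 6). No section describes such a choice, and inspecting every part makes it unlikely. These figures are arithmetic, not an estimate of how this plan would perform.

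The objection also raises practical limits on any remedy, namely consent, specimen condition and SEM coating. They are valid and are built into the fix.

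**Conclusion.** The point holds in a limited form. For a spacer, cord or DTO cord that fails before 12 months, the plan rules out ATR-FTIR and GPC, so a chemical cause can be neither confirmed nor excluded. From 12 months, testing of the failed part is possible but not assured, and GPC never samples a contact or worn area. This does not match the objective to determine causes, or Appendix A's own account of how polymer parts fail.

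No size can be attached: the documents give no expected number of early polymer failures and do not describe how the representative part is chosen. The conclusion rests on the wording of Section 4.3 alone and not on any view of what the cited retrieval studies contained. The primary fusion analysis and the adverse-event comparisons are unaffected. I would class this as a cheap improvement.

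**What to change.** Add to Appendix A, Section 4.3:

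- Any spacer, cord or DTO cord with a structural failure as defined in Section 2 has ATR-FTIR and GPC whatever its time in vivo, where consent and specimen condition allow. Section 3 permits only visual inspection of explants from outside the US without written consent, and rules out investigation of autoclaved polymer parts. Section 4.2.4 keeps only cord spectra with weak or no protein bands, so residual tissue may leave some sites without a usable spectrum.
- Material is taken next to the failure site and at a remote non-contact site of the same part.
- The failed part serves as the representative sample for its system.
- Visual and light-microscope documentation comes first. Material for ATR-FTIR and GPC is then taken before any sputter coating for SEM, or from an uncoated portion, because Section 4.2.3 requires polymers to be coated with carbon or gold.

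Keep the 12-month limit and the current sampling rule for systems with no structural failure.

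The cost is a wording change and a few more runs of assays already specified, on parts already in the laboratory. The downside is slightly more laboratory work and partial consumption of the failed part.
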